7.1.7. Additional Analysis of Adverse Events

7.1.7.1. Stage 3 Opportunistic Illnesses in HIV

On an ongoing basis, AEs will be reviewed for events that might meet the definition of stage 3 opportunistic illnesses in HIV that are indicative of an AIDS-defining diagnoses (see Protocol Appendix 6). The Gilead medical monitor will review the possible stage 3 opportunistic illnesses and approve the events that meet the definition. Events that meet the stage 3 opportunistic illness definition of an AIDS-defining diagnosis will be listed.

7.1.7.2. Cardiovascular or Cerebrovascular Events

Preferred terms for cardiovascular or cerebrovascular events are from relevant Standardised MedDRA Query (SMQ). The selected PT listing was provided by Gilead PVE and reviewed by Gilead medical monitors, which is the same PT listing used to search “Cardiovascular Disease” medical history (see details in [Appendix 3](#)).

The number and percentage of subjects with treatment-emergent cardiovascular or cerebrovascular events and serious cardiovascular or cerebrovascular events by PT will be summarized based on the safety analysis set. A data listing of cardiovascular or cerebrovascular events will be provided.

7.1.7.3. Hepatic Events

Preferred terms for hepatic events are from 15 relevant SMQs, which are identified as non-infectious and non-congenital hepatobiliary disorders. The selected PT listing was provided by Gilead PVE and reviewed by Gilead medical monitors (see details in [Appendix 4](#)).

The number and percentage of subjects with treatment-emergent hepatic events and serious hepatic events by PT will be summarized based on the safety analysis set. A data listing of hepatic events will be provided.

7.2. Laboratory Evaluations

Laboratory data will be analyzed and summarized using both quantitative and qualitative methods using the Safety analysis set. The analysis will be based on values reported in conventional units. When values are below the LOQ, they will be listed as such, and the imputed value will be used for the purpose of calculating summary statistics as specified in Section [3.7](#).

A by-subject listing for laboratory test results will be provided by subject ID number and visit in chronological order for hematology, serum chemistry, and urinalysis separately for all data collected. Values falling outside of the reference range and/or having a severity grade of 1 or higher on the Gilead Grading Scale for Severity of Adverse Events and Laboratory Abnormalities will be flagged in the data listings, as appropriate.

7.2.1. Summaries of Numeric Laboratory Results

Descriptive statistics will be provided for each laboratory test specified in the study protocol as follows:

- Baseline values
- Values at each postbaseline analysis window
- Change from baseline at each postbaseline analysis window
- Percentage change from baseline to each postbaseline analysis window (if specified)

A baseline laboratory value will be defined as the last nonmissing value obtained on or prior to the date of first dose of B/F/TAF. Change from baseline to a postbaseline visit will be defined as the postbaseline value minus the baseline value. The mean, median, Q1, Q3, minimum, and maximum values will be displayed to the reported number of digits; SD values will be displayed to the reported number of digits plus 1.

In the case of multiple values in an analysis window, data will be selected for analysis as described in Section [3.8.3](#).

Calcium Corrected for Albumin

Calcium corrected for albumin will be calculated and summarized for the study. The following formula will be used when both serum calcium and albumin results for a given blood drawn are available and serum albumin value is < 4.0 g/dL.

- Calcium corrected for albumin (mg/dL) = serum calcium (mg/dL) + 0.8 x (4.0 - albumin (g/dL)).

Toxicity grading for calcium will be applied based on the corrected values.

Estimated GFR

The Cockcroft-Gault (CG) formula will be used to calculate eGFR_{CG}:

- eGFR(CG) (mL/min) = $\frac{[(140 - \text{age (yrs)}) \times \text{weight (kg)} \times (0.85 \text{ if female})]}{(\text{SCr (mg/dL)} \times 72)}$, where weight is total body mass in kilograms.

Additionally, for baseline values only, the CKD-EPI (cystatin C) formula will be used to calculate eGFR_{CKD EPI, cysC}:

- eGFR_{CKD EPI, cysC} (mL/min/1.73 m²) = $133 \times \min(\text{Scys}/0.8, 1)^{0.499} \times \max(\text{Scys}/0.8, 1)^{1.328} \times 0.996^{\text{Age}} [\times 0.932 \text{ if female}]$, where Scys is serum cystatin C (mg/L), min (Scys/0.8,1) indicates the minimum of Scys/0.8 or 1, and max (Scys/0.8,1) indicates the maximum of Scys/0.8 or 1.

7.2.2. Graded Laboratory Values

The Gilead Grading Scale for Severity of Adverse Events and Laboratory Abnormalities will be used for assigning toxicity grades (0 to 4) to laboratory results for analysis. Grade 0 includes all values that do not meet the criteria for an abnormality of at least Grade 1. For laboratory tests with criteria for both increased and decreased levels, analyses for each direction (ie, increased, decreased) will be presented separately.

If there is any laboratory toxicity grading scale overlapping with the normal reference ranges (eg, grade 1 scale overlaps with normal reference ranges), laboratory values that are within the normal range will be grade 0, except for lipid tests.

For triglycerides, LDL, and cholesterol, protocol-specified toxicity grading scale is for fasting test values, so nonfasting lipid results (or lipid results without a known fasting status) will not be graded or summarized by toxicity grades.

For the international normalized ratio (INR) of prothrombin time (PT), protocol-specified toxicity grading scale depends on the upper limit of normal range (ULN). While the ULN of INR depends on whether the subject is taking anticoagulant medication or not (ie, Not taking oral anticoagulant: 0.8 – 1.2; Taking oral anticoagulant: 2.0 – 3.0), this information is not collected by the reference laboratory. As a result, INR will be graded by assuming subject is not taking an

oral anticoagulant, which is a conservative approach that may lead to over-reporting of abnormalities for INR. Consequently, INR and PT will not be included in summaries of laboratory abnormalities, but will be included in listings for the following reasons: 1) INR and PT are reflexive tests; 2) only the absolute values, not the toxicity grade, are needed for subject management purposes; and 3) more importantly, the toxicity grades for INR may be over-reported.

7.2.2.1. Treatment Emergent Laboratory Abnormalities

Treatment-emergent laboratory abnormalities are defined as values that increase at least 1 toxicity grade from baseline at any postbaseline time point, up to 30 days from the last dose date of B/F/TAF. If the relevant baseline laboratory value is missing, any abnormality of at least Grade 1 observed within the time frame specified above will be considered treatment-emergent.

Fasting glucose and nonfasting glucose (including glucose results without a known fasting status) are graded based on different grading scales as specified in the protocol.

Treatment-emergent laboratory abnormalities will be summarized for fasting glucose. Maximum postbaseline grade, instead of treatment-emergent grade, for nonfasting glucose (including glucose results without a known fasting status) will be summarized, as nonfasting glucose was not assessed at baseline visit for most of the subjects; therefore, an abnormality is treatment-emergent or not cannot be determined for these subjects.

Both urine RBC based on microscopic examination, labeled as Hematuria (Quantitative), and urine blood based on a dipstick, labeled as Hematuria (Dipstick), are assessed and assigned a toxicity grade in this study. Hematuria (Quantitative) is a reflex test. Urine RBC based on microscopic examination or Dipstick will be presented in laboratory toxicity summary tables and listings.

7.2.2.2. Summaries of Laboratory Abnormalities

The following summaries (number and percentage of subjects) for treatment-emergent laboratory abnormalities will be provided by lab test; subjects will be categorized according to the most severe postbaseline abnormality grade for a given lab test:

- Treatment-emergent laboratory abnormalities
- Treatment-emergent Grade 3 and 4 laboratory abnormalities
- Treatment-emergent Grade 2, 3, and 4 laboratory abnormalities

For all summaries of laboratory abnormalities, the denominator is the number of subjects with any nonmissing postbaseline values up to 30 days after the last dose date of B/F/TAF.

A by-subject listing of all treatment-emergent laboratory abnormalities and treatment-emergent Grade 3 or 4 laboratory abnormalities will be provided by subject ID number and visit in chronological order.

7.2.3. Metabolic Laboratory Evaluations

For metabolic assessments, including fasting glucose and the lipid panel (ie, total cholesterol, triglycerides, LDL, HDL, total cholesterol to HDL ratio), only those measurements under fasting status will be summarized by visit using descriptive statistics. Change from baseline will be tested using the Wilcoxon signed rank test.

In addition, the number and percentage of subjects who took lipid modifying medications at study entry and the number and percentage of subjects who initiated lipid modifying medications during the study will be provided.

A lipid modifying medication is defined as a medication with drug class “LIPID MODIFYING AGENTS” and preferred drug name containing the wording of “STATIN”.

A sensitivity analysis of fasting lipid tests (including total cholesterol, LDL, HDL, triglycerides, and total cholesterol to HDL ratio) will be performed by excluding subjects who took lipid modifying medications at study entry or initiated the medications during the study: baseline, Week 96 and change from baseline at Week 96 will be summarized. Only subjects with both baseline and Week 96 values will be included in the analysis.

Median (Q1, Q3) of change from baseline in fasting metabolic assessments over time will be plotted.

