Appendix 5. Medical History

Number and percentage of subjects with selected medical history of Diabetes Mellitus, Hypertension, Cardiovascular Disease, and Hyperlipidemia will be summarized by treatment as baseline disease characteristics. A subject who had medical history of one of these diseases is a subject who experience at least one of the following events:

- At least 1 medical history record with MedDRA PT (mh.MDRPT) in the selected PT listing for the corresponding disease with start date on or prior to the first dose date.
- At least 1 adverse event record with MedDRA PT (ae.MDRPT) in the selected PT listing for the corresponding disease with start date on or prior to the first dose date.
- At least 1 concomitant medications record with medication class and indication in the following selected listing for the corresponding disease with start date on or prior to the first dose date.

If the start date is incomplete but the month and year (or year alone) of the start date is the same as or before the month and year (or year alone) of the first dosing date of study drug, then the event will be included. If the start date is completely missing, the event will be included.

Four variables (ie, DIABETES, HTENSION, CARDDIS, and HLIPDEM) will be added to raw Medical History and Adverse Events datasets. A medical history or an adverse event record will be flagged for a disease of interest if its MedDRA PT included in the pre-specified PT list for the corresponding disease of interest, which include all PTs from the narrow or broad search of the following SMQs under MedDRA 23.0 provided by Gilead DSPH and reviewed by Gilead medical monitors.

Disease of Interest	SMQ Source
Diabetes Mellitus (DIABETES)	Hyperglycaemia/new onset diabetes mellitus (SMQ) Narrow Scope Term
Hyperlipidemia (HLIPDEM)	Dyslipidaemia (SMQ)
Hypertension (HTENSION)	Hypertension (SMQ)
Cardiovascular disease (CARDDIS)	Ischaemic central nervous system vascular conditions (SMQ) Narrow Scope Term
	Myocardial infarction (SMQ) Narrow Scope Term
	Other ischaemic heart disease (SMQ) Narrow Scope Term

Similarly, four variables (ie, DIABETES, HTENSION, CARDDIS, and LIPMOD) will be added to raw Concomitant Medication dataset. A concomitant medication record will be flagged for a disease of interest if its medication preferred term and indication included in the following listing for the corresponding disease of interest.

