The selected combination of medication preferred term and indication are listed as follows, which was reviewed by Gilead medical monitors.

	Indication (CMINDC)	Preferred Term
Hypertension (HTENSION)		
1	HYPERTENSION	ACETYLSALICYLATE LYSINE
2	HYPERTENSION	ACETYLSALICYLIC ACID
3	ARTERIAL HYPERTENSION	ALFUZOSIN
4	ARTERIAL HYPERTENSION	AMLODIPINE
5	HIGH BLOOD PRESSURE	AMLODIPINE
6	HYPERTENSION	AMLODIPINE
7	HYPERTENSION	AMLODIPINE BESILATE
8	HYPERTENSION	AMLODIPINE BESILATE;INDAPAMIDE;PERINDOPRIL ARGININE
9	ARTERIAL HYPERTENSION	AMLODIPINE BESILATE;PERINDOPRIL ARGININE
10	HIGH BLOOD PRESSURE	AMLODIPINE BESILATE;PERINDOPRIL ARGININE
11	HYPERTENSION	AMLODIPINE;PERINDOPRIL ARGININE
12	HYPERTENSION	BARNIDIPINE HYDROCHLORIDE
13	ARTERIAL HYPERTENSION	BISOPROLOL
14	HYPERTENSION	BISOPROLOL
15	HIGH BLOOD PRESSURE	BISOPROLOL FUMARATE
16	HYPERTENSION	BISOPROLOL FUMARATE
17	ARTERIAL HYPERTENSION	BISOPROLOL FUMARATE;HYDROCHLOROTHIAZIDE
18	HIGH BLOOD PRESSURE	CANDESARTAN
19	HYPERTENSION	CANDESARTAN
20	HYPERTENSION	CELIPROLOL HYDROCHLORIDE
21	HYPERTENSION	DOXAZOSIN MESILATE
22	ARTERIAL HYPERTENSION	EDOXABAN TOSILATE
23	ARTERIAL HYPERTENSION	ENALAPRIL
24	HIPERTENSION	ENALAPRIL
25	ARTERIAL HYPERTENSION	ENALAPRIL MALEATE;HYDROCHLOROTHIAZIDE
26	ARTERIAL HYPERTENSION	HYDRALAZINE HYDROCHLORIDE
27	ARTERIAL HYPERTENSION	HYDROCHLOROTHIAZIDE
28	HYPERTENSION	HYDROCHLOROTHIAZIDE
29	HIGH BLOOD PRESSURE	HYDROCHLOROTHIAZIDE;IRBESARTAN
30	HYPERTENSION	HYDROCHLOROTHIAZIDE;IRBESARTAN
31	HYPERTENSION	HYDROCHLOROTHIAZIDE;OLMESARTAN
32	HYPERTENSION	HYDROCHLOROTHIAZIDE;TELMISARTAN
33	HYPERTENSION	HYDROCHLOROTHIAZIDE;ZOFENOPRIL CALCIUM

	Indication (CMINDC)	Preferred Term
34	ARTERIAL HYPERTENSION	IRBESARTAN
35	HIGH BLOOD PRESSURE	IRBESARTAN
36	HYPERTENSION	IRBESARTAN
37	SYSTEMATIC BLOOD HYPERTENSION	IRBESARTAN
38	HYPERTENSION	ISOSORBIDE MONONITRATE
39	HYPERTENSION	LERCANIDIPINE
40	ARTERIAL HYPERTENSION	LISINOPRIL
41	SYSTEMIC HYPERTENSION	LISINOPRIL
42	ARTERIAL HYPERTENSION	LOSARTAN
43	HYPERTENSION	LOSARTAN
44	HYPERTENSION	NEBIVOLOL HYDROCHLORIDE
45	HYPERTENSION	OLMESARTAN
46	ARTERIAL HYPERTENSION	OLMESARTAN MEDOXOMIL
47	HYPERTENSION	OLMESARTAN MEDOXOMIL
48	ARTERIAL HYPERTENSION	PERINDOPRIL ARGININE
49	HYPERTENSION	PERINDOPRIL ERBUMINE
50	ARTERIAL HYPERTENSION	PHENPROCOUMON
51	ARTERIAL HYPERTENSION	RAMIPRIL
52	HIGH BLOOD PRESSURE	RAMIPRIL
53	HYPERTENSION	RAMIPRIL
54	ARTERIAL HYPERTENSION	TORASEMIDE
55	HIGH BLOOD PRESSURE	URAPIDIL
56	HYPERTENSION	VERAPAMIL
57	HYPERTENSION	ZOFENOPRIL

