	Indication (CMINDC)	Preferred Term
Hyperlipidemia (LIPMOD)		
1	DYSLIPEMIA	ATORVASTATIN
2	DYSLIPIDEMIA	ATORVASTATIN
3	HIPERCHOLESTEROLEMIA	ATORVASTATIN
4	HIPERCOLESTEROLEMIA	ATORVASTATIN
5	HYPERCHOLESTEROLEMIA	ATORVASTATIN
6	HYPERLIPEMIA	ATORVASTATIN
7	HYPERLIPIDAEMIA	ATORVASTATIN
8	HYPERTRIGLYCERIDEMIA	ATORVASTATIN
9	MILD HYPERCHOLESTEROLEMIA	ATORVASTATIN
10	DISLIPEMIA	ATORVASTATIN CALCIUM
11	HYPER COLESTEROLEMY	ATORVASTATIN CALCIUM
12	HYPERCHOLESTEROLEMIA	ATORVASTATIN CALCIUM
13	HYPERCHOLESTEROLEMIE	ATORVASTATIN CALCIUM
14	HYPERTRIGLYCERIDEMIA	GEMFIBROZIL
15	HYPERTRIGLYCERIDEMIA	OMEGA 3 TRIGLYCERIDES
16	DISLIPEMIA MIXTA	PITAVASTATIN
17	ELEVATED LIPIS	PRAVASTATIN
18	ESSENTIAL HYPERCHOLESTEROLEMIA	PRAVASTATIN
19	HYPERLIPEMIA	PRAVASTATIN
20	HYPERCHOLESTEROLEMIA	PRAVASTATIN SODIUM
21	DYSLIPIDEMIA	ROUVASTATIN
22	HYPERCHOLESTEROLEMIA	ROUVASTATIN
23	HIPERCOLESTEROLEMIA	ROUVASTATIN
24	SMALL FIBROUS PLATE	ROUVASTATIN
25	CARDIOVASCULAR PREVENTION	ROUVASTATIN CALCIUM
26	DYSLIPIDEMIA	ROUVASTATIN CALCIUM
27	HIPERCHOLESTERIEMIA	ROUVASTATIN CALCIUM
28	HIPERCHOLESTEROLEMIA	ROUVASTATIN CALCIUM
29	HIPERCHOLESTEROLEMY	ROUVASTATIN CALCIUM
30	HIPERCHOLESTEROLEMIA, CONTINUED ELEVATED LEVELS OF LDL	SIMVASTATIN
31	HYPERLIPEMIA	SIMVASTATIN

	Indication (CMINDC)	Preferred Term
Diabetes Mellitus (DIABETES)		
1	DIABETES MELLITUS TYPE 2	DAPAGLIFLOZIN;METFORMIN
2	MELLITUS DIABETES	EMPAGLIFLOZIN
3	DIABETES MELLITUS	GLICLAZIDE
4	DIABETES MELLITUS	INSULIN GLARGINE
5	MELLITUS DIABETES TYPE II	LINAGLIPPTIN
6	DIABETES	METFORMIN
7	DIABETES MELLITUS	METFORMIN
8	DIABETES MELLITUS TYPE 2	METFORMIN
9	HYPERGLYCEMIA	METFORMIN
10	MELLITUS DIABETES	METFORMIN
11	TYPE 2 DIABETES MELLITUS	METFORMIN
12	DIABETES	METFORMIN EMBONATE
13	DIABETES	METFORMIN HYDROCHLORIDE
14	METABOLE SYNDROME (INSULIN RESISTANCE)	METFORMIN HYDROCHLORIDE
15	MELLITUS DIABETES	METFORMIN HYDROCHLORIDE;SITAGLIPPTIN PHOSPHATE

	Indication (CMINDC)	Preferred Term
	Cardiovascular disease (CARDDIS)	
1	AORTIC VALVE DISEASE	ACENOCOUMAROL
2	ACUTE MYOCARDIAL INFARCTION	ACETYLSALICYLATE LYSINE
3	BIFEMORAL ARTERY BYPASS SURGERY	ACETYLSALICYLATE LYSINE
4	CARDIOPATHY	ACETYLSALICYLATE LYSINE
5	STROKE	ACETYLSALICYLIC ACID
6	MYOCARDIAL INFARCTION	ACETYLSALICYLIC ACID;CLOPIDOGREL BISULFATE
7	ISCHEMIA CARDIOMYOPATHY	AMILORIDE;HYDROCHLOROTHIAZIDE
8	ARYTHMIA	AMIODARONE
9	ATRIAL FIBRILLATION	AMIODARONE
10	CARDIAC RHYTHM DISORDER	AMIODARONE
11	ANGINA	AMOXICILLIN TRIHYDRATE;CLAVULANATE POTASSIUM

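### SAP 7.2.3 calls its variable lipid modifying medication but counts only statins, so users of other lipid drugs alone are uncounted and stay in the lipid sensitivity analysis

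*SAP*

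**What the plan says.** SAP Section 7.2.3 plans to report "the number and percentage of subjects who took lipid modifying medications at study entry", and the corresponding figures for subjects who start such a drug during the study. It then defines the term. The drug must be in class LIPID MODIFYING AGENTS "and preferred drug name containing the wording of" STATIN. The two conditions are joined by 'and', so both must hold.

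The next paragraph uses the same term. It repeats the fasting lipid analysis (total cholesterol, LDL, HDL, triglycerides and the total cholesterol to HDL ratio) by "excluding subjects who took lipid modifying medications at study entry or initiated the medications during the study". It adds a completeness condition: "Only subjects with both baseline and Week 96 values will be included in the analysis".

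SAP Appendix 5 sets a separate flag, LIPMOD, on the concomitant medication data to identify hyperlipidemia history at baseline: "A concomitant medication record will be flagged for a disease of interest if its medication preferred term and indication included in the following listing". The text introducing these lists says of the selection "which was reviewed by Gilead medical monitors". The LIPMOD list contains gemfibrozil (row 14) and "OMEGA 3 TRIGLYCERIDES" (row 15), both with hypertriglyceridemia as the indication.

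Nothing in Section 7.2.3, Appendix 5 or Appendix 7 explains the restriction to statins or widens it.

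**The concern.** The label is broader than the rule behind it. Someone reading the output tables will take lipid modifying medication to mean any lipid drug, and will take the sensitivity analysis to be free of subjects on such drugs. As written, both hold only for statins.

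A subject taking only a non-statin lipid drug would be missing from the usage count that applies (entry or initiator). The same subject would stay in the sensitivity analysis if the fasting baseline and Week 96 values exist. Triglycerides are the most exposed result, because both non-statin entries on the SAP's list were recorded for raised triglycerides.

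The stakes are limited to two descriptive counts and one descriptive sensitivity analysis. The by-visit lipid summaries and their Wilcoxon signed rank tests exclude nobody for medication, so they do not change. The primary and secondary endpoints (Protocol Sections 3.1 and 8.1.3) are not touched.

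**Working it through.** The plan gives no figure of its own to reproduce. The check is a reading of the definition, a text match against the SAP's own drug list, and a sensitivity calculation with assumed inputs.

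**1. Logic of the definition.** Term = (class is LIPID MODIFYING AGENTS) and (preferred name contains STATIN). A non-statin fails the second condition whatever its class. Entry count, initiator count and exclusion all use this term, so a subject taking only a non-statin is outside all three.

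**2. Text match on the LIPMOD list (SAP Appendix 5).**

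| Unit | Total | Without STATIN | Share |
|---|---|---|---|
| Rows | 31 | 2 (rows 14, 15) | 2/31 = 6.5% |
| Distinct preferred terms, as spelled | 10 | 2 | 2/10 = 20% |
| Hypertriglyceridemia rows (8, 14, 15) | 3 | 2 | 2/3 = 67% |

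These are list entries, not subjects. Misspelled free-text indications such as "ELEVATED LIPIS" (row 17) suggest that the list was built from this study's records. It does not show start dates, or whether the gemfibrozil or omega-3 user also took a statin.

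**3. Effect on the usage percentages.** The mock disposition table in SAP Appendix 7 puts 86 subjects in the Safety Analysis Set. For k affected subjects (assumption), the shortfall is k/86:

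- k = 0: 0
- k = 1: 1/86 = 1.2 points
- k = 2: 2/86 = 2.3 points
- k = 3: 3/86 = 3.5 points

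**4. Effect on the sensitivity analysis.** Its size n is not given; 30 to 60 is assumed. One retained user is 1/60 = 1.7% to 1/30 = 3.3% of the set. If that subject's triglyceride change differs from the others' mean by d, the reported mean change moves by d/n:

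- d = 0: no shift
- d = 50 mg/dL, n = 60: 50/60 = 0.8 mg/dL
- d = 200 mg/dL, n = 30: 200/30 = 6.7 mg/dL

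The values of d are assumptions. The median is less sensitive.

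**5. Precision lost by excluding these subjects.** With the standard deviation held constant, the standard error of a mean is multiplied by √(n/(n − k)): √(60/59) = 1.008 for one of 60, and √(30/27) = 1.054 for three of 30. That is an increase of 0.8% to 5.4%.

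**The case against.** The strongest reply is that the rule is explicit and reproducible. It stands in one sentence between the counts and the analysis that use it, and the analysis does exclude users of the term as defined. This is fair for a reader of the SAP. It does not help a reader of a table that carries only the label.

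Second, Appendix 5 is weak evidence of drug class. Its lists identify disease history from drug and indication pairs, and they include drugs with no obvious link to the disease: acetylsalicylic acid under hypertension, omeprazole under cardiovascular disease. The two rules serve different purposes and do not contradict each other. That much stands. Even so, gemfibrozil and omega-3 triglycerides sit under a flag named LIPMOD with hypertriglyceridemia as the indication, so they are not incidental entries.

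Third, a subject on a stable non-statin at both baseline and Week 96 has no obvious drug-driven change, so the shift could be nil. This also stands as a limit on size, and is why d = 0 is shown above. It does not justify the rule, because the SAP chose to exclude statin users at entry as well as initiators.

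Fourth, non-statin use remains visible in the concomitant medication summary and by-subject listing (SAP 7.4.2), and laboratory results are listed by subject (SAP 7.2). True, but those outputs correct neither the counts nor the exclusion.

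Last, a change now might break comparability with the completed Week 24 and Week 48 analyses. The documents do not say which definition those analyses used, so this cannot be judged from them.

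**Conclusion.** The concern holds. As written, any subject taking only a non-statin lipid drug is left out of both usage counts and is not removed from the fasting-lipid sensitivity analysis. This follows from the wording alone and needs no assumption.

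The effect on results is unknown and may be nil. If no such subject exists, only the label is wrong. For one to three subjects, a usage percentage falls short by 1.2 to 3.5 points. One retained subject shifts the mean triglyceride change by 0.8 to 6.7 mg/dL if n is 30 to 60 and d is 50 to 200 mg/dL, and not at all if d is zero. It should be corrected, but no main conclusion of the trial depends on it.

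**What to change.** In Section 7.2.3, delete the STATIN condition. Define a lipid modifying medication as drug class LIPID MODIFYING AGENTS, or any preferred term on the Appendix 5 LIPMOD list, whatever the indication. Apply this to the entry count, the initiator count and the exclusion. Both parts are needed because the documents do not show how every listed drug is classed. Before data finalization, have the medical monitors check the coded concomitant medications for lipid drugs that neither part catches.

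Do not use the LIPMOD drug and indication pairs for this purpose. They would miss statins flagged only on the cardiovascular list: pravastatin for arteriopathy (row 38), and rosuvastatin calcium for acute myocardial infarction (row 42) and for infarction prophylaxis (row 44).

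If a statin-only variable was intended, the minimum is to call it statins in the text and tables, and to state that users of other lipid drugs are not excluded.

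The cost is one sentence, one filter and one term check. The SAP carries August 2020 signatures, so the change needs a SAP revision or, as SAP Section 1 provides, documentation in the clinical study report. If the earlier analyses used the statin-only rule, say so beside the new counts. The sensitivity analysis may lose a few subjects, at the 0.8% to 5.4% increase in standard error shown above for one to three exclusions. Relabelling alone costs almost nothing.
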